1.5 Overall Risks and Benefits

Key study risks are listed below:

- Subjects will have study procedure-related risks:
 - **Blood collection:** The risks of venous blood draws include discomfort at the site of puncture, possible bruising and swelling around the puncture site, rarely an infection; and, uncommonly, fainting, nausea, vomiting, and light-headedness from the procedure.
 - **Muscle biopsy:** The muscle biopsy has potential complications from the procedure that include infection at the biopsy site, bleeding and/or pain at the site of the biopsy, and psychological trauma from the scar at the site of the incision; in some cases, keloid formation can increase scarring.
 - **Cardiac or muscle magnetic resonance imaging (MRI):** The MRI scan is not associated with risks unless a subject has certain types of metal implants such as pacemakers.
 - **Procedural sedation risk:** Sedation risks in children with weak respiratory muscles varies with the medication used. Sedation risks will be explained to the family. Sedation for the imaging must be carefully administered in patients with XLMTM, since most anesthetic agents act directly on the muscle. Bulbar dysfunction, respiratory muscle weakness, gastroesophageal reflux, and scoliosis increase the risk of pneumonia. Children with respiratory and bulbar muscle weakness who are not ventilator dependent may require invasive or noninvasive ventilation after the procedure. The duration of increased ventilatory requirements would vary depending on the degree of respiratory muscle weakness. The potential side effects of specific medications administered for sedation (eg, vomiting, respiratory depression, laryngospasm, emergence reaction), and the likely duration of sedation will be discussed during informed consent for the procedure.
 - **Prophylaxis (prednisolone, ursodiol):** Subjects receive prophylactic prednisolone and ursodiol as part of the clinical study. Information regarding the risks associated with these medications can be found in the respective local prescribing information.
- Overall risks associated with rAAV gene therapy administration include hepatotoxicity, cardiac events such as myocarditis, myositis, thrombocytopenia, thrombotic microangiopathy (TMA), and sensory ganglionopathy ([Arjomandnejad, 2023](#); [FDA, 2021](#); [Lek, 2023](#); [Shen, 2022](#); [Whiteley, 2023](#)).
 - Key identified risks associated with AT132 administration observed in Study ATX-MTM-002 are listed below. Of the overall risks associated with rAAV gene therapy, thrombotic microangiopathy and sensory ganglionopathy have not been observed in ATX-MTM-002 study subjects. Long-term follow-up is important in understanding whether these AEs have long-term implications. Refer to the Investigator's Brochure for further details.
 - **Hepatobiliary events:** Many XLMTM patients have liver dysfunction and cholestasis, which places them at increased risk for hepatobiliary dysfunction or even hepatic failure with rAAV administration. A prospective natural history study (Study ATX-MTM-009) reported that overall, 91% of subjects had histories of hepatic

disease and/or prospectively experienced related AEs or laboratory or imaging abnormalities (Dowling, 2022).

- In Study ATX-MTM-002, SAEs due to hepatobiliary dysfunction occurred after AT132 administration and were characterized by hyperbilirubinemia, cholestatic liver dysfunction, transaminases elevations, ascites, and serum bile acid elevations. Fatal outcomes were observed in 4 subjects due to multifactorial causes including hepatobiliary failure: 1 subject who received the 1.0×10^{14} vg/kg dose and 3 subjects who received the 3.0×10^{14} vg/kg dose. All 4 subjects showed increases in direct and total bilirubin values (> upper limit of normal [ULN]) beginning 1 to 4 weeks after AT132 administration (Shieh, 2023). Liver findings included intrahepatocellular and canalicular cholestasis, periportal and bile ductular reaction, secondary fibrosis, and notable lack of prominent liver parenchymal inflammatory cellular infiltrates (Shieh, 2020).
- **Myocardial events:**
 - *Acute cardiac risks:* Acute myocardial events manifested as myocarditis and increases in troponins. In Study ATX-MTM-002, variable increases in troponin levels after AT132 administration were commonly observed. Two subjects experienced SAEs of myocarditis: 1 subject who received the 1.0×10^{14} vg/kg dose and 1 subject who received the 3.0×10^{14} vg/kg dose. Prolonged prednisolone administration plus addition of other immunosuppressive medications were used for treatment of myocarditis.
 - *Chronic cardiac risks:* Following prolonged immunosuppression for over 3 years, 1 subject experienced an increase in cardiac troponin levels after withdrawal of immunosuppression. Abnormalities in cardiac function have not been observed in this subject. However, long term assessment is required to understand whether there could be more significant impact on cardiac function.
- **Muscle abnormalities:** A skeletal muscle immune response to the rAAV capsid and to the transgene can occur after rAAV gene therapy administration.
 - *Acute and subacute creatine kinase (CK) elevations:* In Study ATX-MTM-002, variable increases in CK levels after AT132 administration were commonly observed, occurring soon after dosing. These CK levels generally returned to normal within the first year after AT132 administration.
 - *Chronic CK elevations and inflammatory infiltrates in skeletal muscles:* Assessment of muscle biopsies demonstrated treatment-associated inflammatory changes in muscle biopsy specimens of some subjects. No SAEs were reported in association to these findings. Improvements in neuromuscular function (respiratory and motor) have been maintained. Although the CK levels generally returned to normal within the first year after AT132 administration, chronic CK elevation over several years can occur.
- **Thrombocytopenia:** Subjects may develop transient thrombocytopenia or decreases in platelet levels from baseline after AT132 administration. In Study ATX-MTM-002, transient thrombocytopenia related to AT132 occurred within the first 2 weeks of dosing (Shieh, 2023).

Key potential study benefits include the following:

- Independent of efficacy, study subjects may receive better-coordinated and more comprehensive overall clinical care at centers of excellence.
- AT132, even if only partially effective, could cause clinically important improvements in respiratory function and mobility and a lowered risk of disease-related comorbidities, leading to greater independence for the subject and caregivers.
- Other patients may benefit from knowledge gained about XLMTM.

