As of Study ATX-MTM-002 protocol v5, the totality of safety, efficacy, and muscle biopsy data collected was assessed to determine the dose of AT132 to carry forward into Part 2 of Study ATX-MTM-002. A statistically significant difference was not observed between dose levels (1.0×10^{14} vg/kg and 3.0×10^{14} vg/kg) in the respiratory and neuromuscular endpoints. At Week 24, myotubularin protein expression reached or exceeded normative levels in Cohort 2 subjects who all were administered 3.0×10^{14} vg/kg AT132, and there was an indication of a faster rate of histopathological improvement at this dose. AT132 was well-tolerated with a manageable safety profile across both Cohort 1 and Cohort 2 in Part 1. However, in subjects treated with 3.0×10^{14} vg/kg, there was an indication of potential dose-related adverse events (AEs) (eg, transient decrease in platelet counts, and exacerbation of preexisting hyperbilirubinemia) that could increase in frequency and magnitude should dose escalation continue. Based on these data, the Sponsor, in conjunction with the DMC, agreed that it would not be in the best interest of patient safety to continue with dose escalation beyond the 3.0×10^{14} vg/kg dose level; therefore, dose escalation to the planned 5.0×10^{14} vg/kg dose level (ie, Cohort 3) did not occur. The dose of AT132 selected to be carried forward into Part 2 was 3.0×10^{14} vg/kg.

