Clinical significance of out-of-range laboratory findings is to be determined and documented by the Investigator or Sub-Investigator who is a qualified physician. Abnormal laboratory findings associated with the underlying disease are not considered clinically significant unless judged by the Investigator to be more severe than expected for the subject's condition.

Laboratory abnormalities that are considered to be clinically significant by the Investigator must be recorded as AEs. Laboratory abnormalities (eg, clinical chemistry, hematology, coagulation parameters, and urinalysis) that require medical or surgical intervention must be recorded as an AE, as well as an SAE if the abnormality meets SAE criteria (defined in [Section 6.2.1](#)). In addition, laboratory or other abnormal assessments (eg, ECG, X-rays, vital signs) that are associated with signs and/or symptoms must be recorded as an AE or SAE if they meet the definition of an AE or SAE as described in [Sections 6.1.1](#) and [6.2.1](#), respectively. If the laboratory abnormality is part of a syndrome, record the syndrome or diagnosis (eg, anemia), not the laboratory result (eg, decreased hemoglobin).

The following laboratory abnormalities should be recorded as AEs regardless of whether considered to be clinically significant, unless the abnormality is considered to be part of an integrated diagnosis:

- Troponin I or Troponin T values above the ULN (or a non-zero value if no ULN is reported) for which additional diagnostic workup and/or treatment is indicated per consultation with the site pediatric cardiologist (see [Section 4.6.1](#))
- Platelet values below the lower limit of normal, or below the subject's baseline value if abnormal at baseline

Please contact the Medical Monitor if there are questions regarding how to capture laboratory abnormalities.

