3.0	10-Jan-2024	Main Analytical Approach of Secondary Endpoints (4.4.2.2)	Additional details added regarding analysis. Aligned to protocol V 11.0. Removed comparisons between groups. Removed correlation analysis. Updated scoring algorithms to align with scoring instructions. Removed logic for deriving missing motor developmental milestones and wording around adjudication of motor milestones.	Aligning SAP to protocol Amendment version 11.0; adding details for clarity of definitions
3.0	10-Jan-2024	Main Analytical Approach of Exploratory Endpoints (4.5.1.2)	Additional details added regarding analysis. Aligned to protocol V 11.0. Removed comparisons between groups. Removed correlation analysis. Updated scoring algorithms to align with scoring instructions. Removed analysis of subscores for questionnaires.	Aligning SAP to protocol Amendment version 11.0; adding details for clarity of definitions

SAP Version	Approval Date	SAP Section(s)	Change	Rationale
3.0	10-Jan-2024	Safety Analysis (4.6)	Removed Interferon-gamma and developmental parameters endpoints. Added hospitalization rate and annualized respiratory and non-respiratory SAE rate, and length of stay per hospitalization as endpoints.	Aligning SAP to protocol Amendment version 11.0
3.0	10-Jan-2024	Adverse events (4.6.1)	Added definitions of periods as well as analysis by period. AESI definitions have been updated. Additional AE summaries have been added. Additional details added on the AE analysis. Addition of swimmer plots and COVID-19 analysis.	Definitions aligned to the investigator brochure as well as more clearly described. Modifications made for more interpretable analysis.
3.0	10-Jan-2024	Additional Safety Assessments (4.6.2)	Additional detail and clarifications added to align with Protocol Version 11.0. Liver safety assessments section added. Developmental parameters section removed. Added liver safety analysis. Vital sign and ECG threshold criteria and analyses updated.	Aligning SAP to protocol Amendment version 11.0. Modifications made for more interpretable analysis.
3.0	10-Jan-2024	Biodistribution and Viral Vector Shedding (4.7.1.2)	Updated analyses to correspond to what is considered meaningful.	Aligning SAP to data needed for the label.
3.0	10-Jan-2024	Subgroup Analysis (4.7.2)	Subgroup analyses have been removed	Aligning SAP to protocol Amendment version 11.0

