In the participant count, if a participant has multiple TEAEs with the same SOC or PT, but with differing severity, relationship, or action taken, then the participant will be counted once with the worst nonmissing severity grade, highest degree of relationship, or highest severity of action taken (Not Applicable < Dose Not Changed < Drug Interrupted < Drug Withdrawn). If severity, relationship, or action taken is missing for all episodes of the event, the participant will be counted under missing severity, relationship, or action taken. This summary will only be created for the ‘overall’ period.

The following adverse events of special interest (AESI) are defined by the following categories and corresponding MedDRA Version 26.0 SMQ search criteria. If MedDRA Version is upgraded, then the search criteria will be correspondingly upgraded to align with the updates:

- **Muscle abnormalities**
 - Rhabdomyolysis/myopathy (SMQ, broad and narrow)
 - Investigations (SOC)

- Investigations, imaging and histopathology procedures (HLGT)
- **Myocarditis**
 - Noninfectious myocarditis/pericarditis (SMQ - broad)
- **Hepatobiliary disorders**
 - Hepatic Disorders (SMQ – broad)
 - Drug related hepatic disorders (SMQ - broad)
 - Cholestasis and jaundice of hepatic origin (SMQ - broad)
 - Drug related hepatic disorders - severe events only (SMQ - broad)
 - Liver related investigations, signs and symptoms (SMQ - broad)
 - Liver-related coagulation and bleeding disturbances (SMQ - broad)
 - Biliary disorders (SMQ - broad)
 - Functional, inflammatory and gallstone related biliary disorders (SMQ - broad)
 - Biliary system related investigations, signs and symptoms (SMQ - broad)
 - Biliary tract disorders (SMQ - broad)
 - Gallbladder related disorders (SMQ - broad)

The number and percentage of participants with AESIs, as classified by AESI category, SOC and PT will be summarized for each treatment group and overall. Summaries will be provided for the following:

- TEAEs
- Drug related TEAEs,
- Serious TEAEs,
- Drug related serious TEAEs,
- Grade 3 or higher TEAEs,
- Grade 3 or higher related TEAEs

Swimmer plots will be created, which will include information on glucocorticoid dosing (dose/duration) and AESI occurrence.

All AESIs will be listed.

All AEs that correspond to the MedDRA COVID-19 narrow SMQ search term will be listed separately.

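### Of the protocol's four key identified risks, only thrombocytopenia has neither an AESI category nor a laboratory threshold in the SAP, so no grouped AE rate or worst platelet laboratory grade per child is planned by dose

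*Protocol*

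**What the plan says.** Protocol 1.5 introduces its list with "Key identified risks associated with AT132 administration observed in Study ATX-MTM-002 are listed below". It then gives four headings: hepatobiliary events, myocardial events, muscle abnormalities and thrombocytopenia. Under the last it says "Subjects may develop transient thrombocytopenia or decreases in platelet levels from baseline after AT132 administration", and places the related events in the first two weeks after dosing.

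Protocol 1.4.2, explaining why escalation stopped, refers to "potential dose-related adverse events (AEs) (eg, transient decrease in platelet counts" at the higher dose.

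Protocol 6.4 requires certain laboratory findings to be recorded as AEs whatever their clinical significance, unless they belong to an integrated diagnosis. One of them is "Platelet values below the lower limit of normal, or below the subject's baseline value if abnormal at baseline".

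SAP 4.6.1 states: "The following adverse events of special interest (AESI) are defined by the following categories and corresponding MedDRA Version 26.0 SMQ search criteria". Three categories follow: muscle abnormalities, myocarditis and hepatobiliary disorders. Each gets six summaries by dose group, and AESIs also feed the swimmer plots and a listing. The SAP's version history gives the basis for the AE definitions as "Definitions aligned to the investigator brochure as well as more clearly described".

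SAP Table 4 (potentially clinically significant laboratory values) has hemoglobin and hematocrit under hematology, and no platelet row.

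**The concern.** SAP 1.3 says the intent is now to describe safety and efficacy in children given the low or the high dose. A risk that the protocol calls identified, and whose example it gives as possibly dose related, should therefore be easy to read by dose. Three of the four risks have a pre-specified grouping of terms and at least one laboratory threshold. Thrombocytopenia has neither. A reader wanting the proportion of children affected at each dose, and how severely, would have to assemble it from separate rows and visits, and may not be able to do so exactly.

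**Working it through.** No figure in the plan needs reproducing. The check sets the risk list against the planned outputs.

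**1. Coverage of the four risks**

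| Key identified risk (Protocol 1.5) | AESI category (SAP 4.6.1) | Marker in SAP Table 4 |
|---|---|---|
| Hepatobiliary | Yes | ALT, AST (and all of Table 5) |
| Myocardial | Yes | Troponin T and I |
| Muscle | Yes | CK |
| Thrombocytopenia | No | None |

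Table 4 has 9 chemistry rows (sodium, potassium, bicarbonate, creatinine, CK, ALT, AST, glucose, troponin) and 2 hematology rows: 9 + 2 = 11, with 0 for platelets.

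**2. What is planned for platelets**

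- SAP 4.6.1: number and percentage of children with each preferred term, by dose group and overall, with drug-related, serious and Grade 3 or higher versions. The rule for repeated events takes a child's worst AE grade within an SOC or preferred term.
- SAP 4.6.2.1: number and percentage below the reference range by dose and visit; CTCAE grade by visit; and a grade shift from baseline by dose and parameter. Protocol 7.4.1.2 describes the shift as an increase of at least one grade at any time after baseline. Platelet count is in the hematology panel (Protocol Appendix 1).

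None of these groups related platelet terms. No laboratory table takes each child's lowest platelet value and grades it. The shift table combines small and large falls in one count.

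**3. What separate preferred-term rows can show**

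Protocol 6.4 says to record a diagnosis instead of the laboratory result where the abnormality is part of a syndrome. Protocol 6.5.3.1 grades laboratory abnormalities reported as AEs under the Investigation class. The same fall could therefore be recorded as a diagnosis or as a finding. If a and b children fall under two terms among n, the number affected lies between max(a, b) and min(n, a + b).

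Illustration (a and b are assumed; n = 17 is the high-dose count in Protocol 1.4.2 at the 08 July 2020 cutoff): with a = b = 3, the bounds are 3/17 = 17.6% and 6/17 = 35.3%.

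Weight of one child: 1/17 = 5.9% at the high dose. For the low dose, Protocol 1.4.2 gives 6 treated. Three controls were then undosed (Protocol 3.1), and SAP 1.3 excludes two never dosed, which leaves 3 − 2 = 1 more. So n = 6 + 1 = 7 if no replacement child was enrolled, and 1/7 = 14.3%.

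**4. Whether by-visit tables catch a brief nadir**

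SAP 4.10.2 keeps the value closest to the scheduled day. In SAP Table 10 the hematology windows are Days 1–4 (Day 2), 5–10 (Week 1) and 11–21 (Week 2). If samples exist on Days 7 and 10, both fall in Week 1. The Day 7 value (distance 0) is kept and the Day 10 value (distance 3) is dropped, even if it is the nadir.

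SAP 4.6.2.1 also prefers central over local results where both exist. Protocol 5.1.1.8 recommends local laboratories for Weeks 1 to 16 but sends home-nurse samples to the central laboratory, so both can occur in one window. By contrast, SAP 4.6.2.2 summarises liver tests by each child's highest post-dose value from all laboratories.

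**5. The muscle category**

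The muscle AESI lists the Investigations system organ class on its own line, followed by a high-level group term for imaging and histopathology. Read literally, the first line would count a platelet finding coded to Investigations as a muscle abnormality. If that line only marks where the group term sits, it would not. The SAP does not say which is meant.

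**The case against.** The strongest reply is that platelet events will not be hidden. Protocol 6.4 sends low values into the AE database, SAP 4.6.1 tabulates every preferred term by dose, and the grade-shift table gives one platelet rate per dose that term coding cannot split. All of this stands. A reader might infer that no AE table shows any proportion of affected children by dose; the documents contradict that.

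A second reply is that a key identified risk need not be an AESI. Protocol 6.5 and 4.6 centre on cardiac, liver, immune and neuromuscular events, and the SAP says it followed the Investigator's Brochure. This explains the choice, and no passage requires every key risk to be an AESI. It does not explain why one of four listed risks, with a stated possible dose relation, is summarised less fully. Nor does timing settle it: SAP v4.0 (15 April 2024) predates protocol v12 (17 May 2024), yet its version history records a change made to align with v12.

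A third reply is that splitting across terms is conjecture and that Protocol 6.1.3.3 and 6.4 favour recording a diagnosis. That is fair. The 3 and 3 split is assumed, and the documents do not show that the signal is in fact split or understated. Table 4 covers only selected tests, so the absence of a platelet row is a gap in coverage, not an error.

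Finally, the study is small, descriptive and has full listings, so a reader could count by hand. This lowers the stakes but does not provide a pre-specified count.

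**Conclusion.** The omission is real and limited. Thrombocytopenia is the only one of the four key identified risks with neither an AESI category nor a Table 4 threshold (1 of 4 risks; 0 of 11 rows). Preferred-term rates, below-range counts and a one-grade shift rate are planned by dose. A grouped AE rate and each child's worst post-dose platelet laboratory grade are not. The worst AE grade is taken only within a term or class, so it helps only if all events share one.

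The 17.6% to 35.3% range rests on assumed counts and on events being coded to two terms. The nadir concern requires more than one result in a window. The muscle-category concern depends on a literal reading of one line. Because the data are collected and partly tabulated by dose, severity is minor to moderate.

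**What to change.** In SAP 4.6.1, add a thrombocytopenia AESI category, defined by a standard SMQ or a listed set of preferred terms that covers both the diagnosis and the laboratory-finding terms. Give it the same six summaries, the swimmer plot and the listing. Restrict the Investigations line under muscle abnormalities so that it cannot capture platelet terms.

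In SAP 4.6.2.1, add a platelet summary by CTCAE grade, which the SAP already applies to laboratory results. Use each child's lowest post-dose value from any laboratory, by dose group, as the liver section already does with the highest value.

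The cost is a small amount of programming on existing table shells. No new data are needed.

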2 STUDY OBJECTIVES, ENDPOINTS, AND ESTIMANDS

The objectives of the study are as follows:

- To determine the therapeutic dose of AT132
- To confirm the safety and efficacy of the therapeutic dose of AT132

The endpoints of the study are as follows:

Primary Efficacy Endpoint:

- Change from baseline in hours of ventilation support at Week 24

Key Secondary Efficacy Endpoint:

- Percentage of subjects achieving functionally independent sitting for at least 30 seconds at Week 24

Other Secondary Efficacy Endpoints:

- Time to reduction in required ventilator support to \leq 16 hours a day (only in subjects who require invasive ventilation) at Week 24
- Change from baseline in CHOP INTEND at Week 24
- Change from baseline in maximal inspiratory pressure (MIP) at Week 24
- Change from baseline in quantitative analysis of myotubularin expression in the muscle biopsy at Week 24
- Change from baseline in quality of life assessments at Week 24 (ie, the Assessment of Caregiver Experience with Neuromuscular Disease (ACEND) and Pediatric Quality of Life Inventory (PedsQL))
- Number (%) of age-appropriate clinically relevant gross motor function milestones attained through Week 24
- Percentage of subjects achieving full ventilator independence at Week 24
- Survival

Safety Endpoints:

- AEs, SAEs, and findings from safety laboratory tests, 12-lead electrocardiogram (ECG), echocardiograms (ECHOs), vital signs, growth parameters, physical examinations, liver ultrasounds, antibody formation (anti-AAV8, anti-MTM1), viral shedding, annualized hospitalization rate, annualized respiratory and non-respiratory SAE rate, and length of stay per hospitalization

Exploratory Endpoints:

- Time to unassisted sitting for 30 seconds or more at Week 24
- Change from baseline in the Motor Function Measure-32 (MFM-32) at Week 24
- Change from baseline in total raw score in the gross motor domain of the Bayley Scales of Infant and Toddler Development III (Bayley-III) at Week 24

- Change from baseline in total raw score in the fine motor domain of the Bayley-III at Week 24
- Change from baseline in the proportion of patients being able to feed without a gastrostomy or G-tube at Week 24
- Change from baseline in the Communicative Development Inventories scores at Week 24
- Change from baseline in the Parental Global Impression of Secretion Severity (PGIS-S) score at Week 24
- Change in the Parental Global Impression of Secretion Improvement (PGIS-I) score at Week 24
- Change from baseline in Clinical Global Impression of Severity (CGI-S) at Week 24
- Change in the Clinical Global Impression of Improvement (CGI-I) score at Week 24

